425 tDCS effects from the first visit dissipated, and the first simulation visit was expected to occur 7
426 days after the enrollment visit (average days = 13.59 days in the current study).

Day 1 —→ Day 2-8 —→ Day 9 —→ Day 10-16 —→ Day 17 —→ Day 18-24

427

[figure not shown]
428 **Figure 1. Flowchart of the study procedure**

429

430 **6. Stimulation Protocol**

431 *6.1 Stimulation Procedure*

432 After completing pre-stimulation assessments, participants started the first stimulation
433 procedure of the visit via neuroConn's programmable Direct Current stimulator. Electrodes were
434 affixed to the participant's head to target the stimulation area as determined for each individual
435 via the international 10-20 EEG placement system with Modified Combinatorial Nomenclature.
436 For stimulating the right VLPFC, the anode was placed over F6 (Montreal Neurological Institute
437 coordinates: 44, 32, -12 (Pinkham, Hopfinger, Ruparel, et al., 2008), and the contralateral
438 homolog area (F5) was targeted for the stimulation of the left VLPFC (see **Figure 2** for 10-20
439 EEG placement). Electrodes were placed identically for the control condition. Following the
440 neurostimulation procedure, participants were asked to remain seated in the chair and browse
441 through magazines quietly for 30 minutes to allow stimulation effects to stabilize (Samani et al.,
442 2019).

443

444 **Figure 2. 10-20 EEG placement**

[figure not shown]
445 6.2 Counterbalance and Randomization

446 The active stimulation and sham control conditions were counterbalanced, meaning that
447 each participant had the same possibility of experiencing either the active or sham condition at
448 the first visit, and the other condition at the second visit. In the current study, 26 participants
449 received the active stimulation at their Visit 1, while the remaining 24 received it at their Visit 2.
450 This counterbalance procedure was achieved via the “study mode” preprogrammed feature of the
451 NeuroConn machine, which randomly assigned participants to either the active stimulation or
452 sham group in a double-blinded way. Specifically, each participant received a 5-digit code,
453 which was paired with one active stimulation code and one sham control code to ensure that each
454 participant did not receive two stimulation or control conditions. After study completion, each
455 participant’s study code for that given visit was revealed and recorded. The project manager
456 maintained the list containing the condition information corresponding to each visit during the
457 study in case the blind conditions needed to be revealed in real time (e.g., if participants reported
458 adverse effects during tDCS).

459 *6.3 Stimulation Parameters*

The total stimulation time of 40 minutes was divided into two twenty-minute sessions to allow repeated stimulation, which may increase efficacy (Cheng et al., 2020; Kim et al., 2019). The active stimulation included active current at 2mA, ramping up over 15 seconds, sustaining for 20 minutes, and finally ramping down for 15 seconds. The dimensions of each electrode were 5 × 7 centimeters in size (35 cm^2), which led to a current density of 0.5714 mA/cm². For the sham condition, electrodes were still attached for 20 minutes each session, but the actual stimulation time was limited to 45 seconds per session, with 15 seconds of gradual stimulation, leading up to 15 seconds of full stimulation, and finally 15 seconds of ramping down. This limited stimulation mimicked the ramp up phase of active stimulation, making it more difficult for participants to guess the condition. The machine also automatically performed impedance control checks throughout the neurostimulation to ensure that both the participant and the experimenter could not tell which condition was being administered. Following each session,

472 inquiries into the participants' perceptions of the suspected condition showed that their accuracy
473 in identifying the correct condition was below chance levels (47%), supporting the efficacy of
474 the blinding procedures.

475

476 **Figure 3. Computational simulation of tDCS-induced current density.** (A) shows the
477 montage location in the study (1 = right VLPFC, 2 = left VLPFC). (B) reveals the distribution of
478 the current density estimated based on the stimulation location and parameters.

479

480 6.4 Current Modeling

481 To better characterize the current distribution during the stimulation, current modelling
482 was conducted for the active condition. This computational simulation utilized a finite element
483 model derived from MRI, implemented through the Comets toolbox (Jung et al., 2013) in Matlab
484 (<http://www.COMETStool.com>). **Figure 3** illustrates a detailed three-dimensional (3D)
485 numerical analysis of the current density generated by tDCS based on the montage applied in this
486 study. It reveals that our targeted VLPFC is one of the regions receiving the most intense
487 stimulation, along with the dorsal medial PFC and a portion of the DLPFC.

488

489 7. Assessments

490 7.1 Enrollment Visit

491 At the enrollment visit, consent was obtained from participants, and demographic
492 information was also collected. Paranoia screening and diagnostic interviews were performed to
493 determine eligibility. Current medications were reported by the patients, and they were asked to

494 remain on a stable dose of medication throughout their participation in the study unless
495 specifically recommended by their physician. After that, participants completed daily EMA
496 surveys for 7 days to assess baseline paranoia level and social functioning in daily life. They then
497 attended the first stimulation visit. At both stimulation visits, the Positive and Negative
498 Syndrome Scale (PANSS) (Kay et al., 1987) was administered by trained research personnel to
499 assess the full range of symptoms in individuals with SSD. Daily EMA surveys between
500 Stimulation Visit 1 and 2, as well as after Stimulation Visit 2, were also sent to participants to
501 monitor any changes in paranoia and social functioning after tDCS in the participant's day-to-
502 day life.

503 *7.2 Stimulation Visits: Pre-stimulation Assessments*

504 **Trait Paranoia.** The Paranoia Scale (PS) (Fenigstein & Venable, 1992) is a self-report
505 measure to assess trait paranoia. This measure contains 20 items (e.g., "Someone has it in for
506 me", "It is safer to trust no one") and is measured on a five-point Likert scale (1 = not at all
507 applicable, 5 = extremely applicable). Scores range from 20-100, with higher scores indicating
508 higher paranoia. The PS demonstrated good reliability and validity in previous work on patients
509 with schizophrenia (Pinkham et al., 2012; Tiernan et al., 2014). In the current study, PS showed
510 excellent internal consistency in both Stimulation Visit 1 (Cronbach's $\alpha = 0.941$) and Stimulation
511 Visit 2 (Cronbach's $\alpha = 0.930$).

512 **State Paranoia.** The State Social Paranoia Scale (SSPS) (Freeman et al., 2007) was used
513 to examine paranoia levels immediately before and at the conclusion of stimulation within each
514 visit. Participants indicated how much they agreed with each of 20 statements (e.g., "Someone
515 was hostile towards me", "Someone was trying to isolate me") using a five-point Likert scale (1
516 = do not agree, 5 = totally agree). Additionally, the SSPS contains three subscales, measuring
517 paranoid, neutral, and positive thinking. Scores range from 20-100, and higher scores represent
518 higher state paranoid ideation. Acceptable reliability and validity have been demonstrated in
519 previous research in patients with psychosis (Freeman et al., 2015; Veling et al., 2016). In the
520 current study, the total scale (Visit 1: Cronbach's $\alpha_{pre} = 0.819$, Cronbach's $\alpha_{post} = 0.840$; Visit 2:
521 Cronbach's $\alpha_{pre} = 0.798$, Cronbach's $\alpha_{post} = 0.880$) and the persecution subscale scale (Visit 1:
522 Cronbach's $\alpha_{pre} = 0.924$, Cronbach's $\alpha_{post} = 0.926$; Visit 2: Cronbach's $\alpha_{pre} = 0.903$, Cronbach's
523 $\alpha_{post} = 0.911$) showed outstanding internal consistency. The neutral thinking (Visit 1: Cronbach's
524 $\alpha_{pre} = 0.750$, Cronbach's $\alpha_{post} = 0.457$; Visit 2: Cronbach's $\alpha_{pre} = 0.603$, Cronbach's $\alpha_{post} = 0.803$)
525 and positive thinking (Visit 1: Cronbach's $\alpha_{pre} = 0.706$, Cronbach's $\alpha_{post} = 0.731$; Visit 2:
526 Cronbach's $\alpha_{pre} = 0.611$, Cronbach's $\alpha_{post} = 0.853$) subscales showed mostly acceptable internal
527 consistency.

528 **State Anxiety.** Considering that anxiety has been consistently identified as a construct
529 that overlaps with paranoia (Martin & Penn, 2001; Startup et al., 2007), we also measured state
530 anxiety to examine potential changes after tDCS. The State subscale of State-Trait Anxiety
531 Inventory (STAI-S) includes 20 items measuring current feelings (e.g., "I am tense", "I feel
532 nervous") on a four-point Likert scale (1 = not at all, 4 = very much so; scores range 20-80)
533 (Spielberger, 2010), with higher scores indicating higher anxiety at this moment. The STAI-S
534 demonstrated excellent internal consistency in both visits (Visit 1: Cronbach's $\alpha_{pre} = 0.879$,
535 Cronbach's $\alpha_{post} = 0.869$; Visit 2: Cronbach's $\alpha_{pre} = 0.847$, Cronbach's $\alpha_{post} = 0.908$).

536 *7.3 Assessments Between the Two Stimulation Sessions*

537 As noted, participants were asked to sit quietly for 30 minutes after each stimulation

538 session to enable the stimulation to work thoroughly throughout the neural networks. Next, they
539 completed several assessments of basic cognitive function and social cognitive ability/bias that
540 have been generally linked to psychotic symptoms and paranoia but that were not of primary
541 importance and therefore not reported here. Relationships among paranoia, social decision-
542 making, and aggression were also explored in this segment for secondary analyses. Since these
543 analyses were not the main focus of the project, they are not included in the main text (details of
544 all measures administered between stimulation sessions can be found in **Appendix A**).

545 Participants were offered a 30-minute break before the second stimulation session of that visit.
546 The only measure relevant to the main goal of this study is overall social functioning as detailed
547 below:

548 ***Birchwood Social Functioning Scale (SFS; Stimulation Visit 1 and 2).*** The SFS
549 (Birchwood et al., 1990) measures 7 domains of social adjustment based on self-reports (range =
550 0-223, Cronbach's $\alpha_{\text{visit 1}} = 0.915$, Cronbach's $\alpha_{\text{visit 2}} = 0.897$), including social
551 engagement/withdrawal (range = 0-15; Cronbach's $\alpha_{\text{visit 1}} = 0.422$, Cronbach's $\alpha_{\text{visit 2}} = 0.561$),
552 interpersonal communication (range = 0-9; Cronbach's $\alpha_{\text{visit 1}} = 0.426$, Cronbach's $\alpha_{\text{visit 2}} = 0.269$),
553 prosocial activities (range = 0-66; Cronbach's $\alpha_{\text{visit 1}} = 0.879$, Cronbach's $\alpha_{\text{visit 2}} = 0.815$),
554 recreation activities (range = 0-45; Cronbach's $\alpha_{\text{visit 1}} = 0.684$, Cronbach's $\alpha_{\text{visit 2}} = 0.749$),
555 independence-competence (range = 0-39; Cronbach's $\alpha_{\text{visit 1}} = 0.911$, Cronbach's $\alpha_{\text{visit 2}} = 0.934$),
556 independence-performance (range = 0-39; Cronbach's $\alpha_{\text{visit 1}} = 0.915$, Cronbach's $\alpha_{\text{visit 2}} = 0.920$),
557 and employment (single item; range = 0-10). A higher score on each subscale indicates better
558 functioning in the respective social domain, while a higher overall score signifies better social
559 functioning in general. The SFS was originally developed for schizophrenia patients and has
560 been widely used to measure social functioning outcomes in this population (Birchwood et al.,
561 1990; Burns & Patrick, 2007).

562 *6.7 Stimulation Visits: Post-stimulation Assessments*

563 ***State Paranoia and State Anxiety.*** SSPS and STAI-S were administered as described in
564 the pre-stimulation assessments.

565 ***Ambiguous Intentions Hostility Questionnaire (AIHQ).*** The AIHQ is a widely used
566 measure to assess hostile attributional style in ambiguous situations (Combs et al., 2007). It is
567 selected as one of the primary outcome measures because hostile perception is a crucial
568 component of paranoia (Combs et al., 2009; Zaytseva et al., 2013), and there is a robust,
569 medium-to-large association between paranoia and hostile attributional bias measured by AIHQ
570 (r fluctuates at around 0.3-0.5) (An et al., 2010; Combs et al., 2009; Klein et al., 2018; Langdon
571 et al., 2013). Five ambiguous scenarios were presented to participants, and they gave reasons
572 why each situation happened, indicated how much they thought that people did this to them on
573 purpose, how angry they would be, how much they would blame others, and what they would do
574 about it. Responses to the first and last questions were recorded verbatim for later coding, and
575 responses to questions 2-4 were rated on Likert scales (1-6 for if the behavior was on purpose
576 and 1-5 for how angry they were and how much they would blame others). These three Likert
577 scale items were averaged to form the blaming attribution subscale of AIHQ, which showed

578 outstanding internal consistency in both visits (Cronbach's $\alpha_{\text{visit 1}} = 0.905$, Cronbach's $\alpha_{\text{visit 2}} = 0.901$). For the open-ended questions, hostility and aggression biases were rated by three
579 independent, trained raters using a five-point Likert scale (1 = not hostile/aggressive at all, 5 =
580 very hostile/aggressive). Inter-rater reliability was computed by ICC among all the raters, with
581 ICC $> .80$ being acceptable (ICC = 0.892 in the present study). Thus, the AIHQ yielded three
582 summary scores, the Blaming Score, the Hostility Bias Score, and the Aggression Bias Score.
583

584 **Scrambled-sentences task (SST):** In the SST (Wenzlaff, 1993), participants reordered
585 strings of scrambled words to create sentences of either paranoid or nonparanoid meanings by
586 selecting 5 out of the 6 provided words. For example, participants could reorder the words from
587 "Winner, am, born, I, loser, a" to "I am a born winner" (positive interpretation) or "I am a born
588 loser" (negative interpretation). They were given 4 min to finish as many as possible. The total
589 number of paranoid sentences was divided by the total number of completed sentences and then
590 multiplied by 100 to generate a percentage bias score, with a greater percentage indicating a
591 higher level of paranoid interpretation bias. Previous research has demonstrated moderate-to-
592 strong correlations between SST scores and paranoia (r fluctuates at around 0.4-0.6) (Savulich et
593 al., 2015, 2017).

594 **Hostility Scale of the Personality Inventory for DSM-5 (PID-5-HS):** PID-5-HS
595 (Krueger et al., 2012) contains 10 self-report items (e.g., "I snap at people when they do little
596 things that irritate me") assessing pathological hostility on a 4-point scale (0 = very false or often
597 false, 3 = very true or often true), with higher total scores indicating more hostility (range = 0-
598 30). PID-5-HS showed a high correlation with AIHQ blame score ($r = 0.47$) in previous research
599 (Buck et al., 2016). In the current study, the internal consistency of PID-5-HS was excellent
600 (Cronbach's $\alpha_{\text{visit 1}} = 0.902$, Cronbach's $\alpha_{\text{visit 2}} = 0.913$).

601 **Trustworthiness Task.** The trustworthiness task requires participants to indicate how
602 much they trust each of 60 grayscale facial stimuli along a 7-point Likert scale (-3 = very
603 untrustworthy, 3 = very trustworthy) (Adolphs et al., 1998). Total scores were calculated by
604 averaging across responses and hence varied from -3 to +3, with higher values indicating a
605 greater tendency to trust others. There is a small-to-medium association between trustworthiness
606 scores and paranoid ideation (r fluctuates between -0.1 and -0.3) (Buck et al., 2016; Klein et al.,
607 2018).

608

609 **8. Ecological Momentary Assessments**

610 EMA surveys were administered for a total of 21 days – 7 days prior to simulation visit 1,
611 7 days after stimulation visit 1, and 7 days after stimulation visit 2. Participants received 3
612 randomly timed surveys assessing current paranoid symptoms and social interactions each day.
613 The surveys were sent in the morning, mid-day, and evening, with random initiation at time
614 intervals ≥ 2 hours. Participants were allowed to respond to the survey within 1 hour after the
615 survey was sent. This protocol is in line with previous work and was demonstrated to yield ideal
616 intra-day variation and compliance (Jones, Moore, Depp, et al., 2021; Jones, Moore, Pinkham, et
617 al., 2021). Each survey queried the frequency of auditory hallucinations and paranoid ideation
618 along a 7-point scale, as well as the emotions associated with and perceptions of social
619 interactions since the last survey (e.g., did you interact with anyone since your last survey?).
620 Affective states since the past alarm were rated on a 7-point scale using the following items:
621 sad/depressed, excited, irritated, happy, belongingness, and burden to others. Expectations

622 regarding subsequent interpersonal situations were also rated on a 7-point scale (e.g., how much
623 interest do you have in interacting with people for the rest of the day?). **Appendix B** contains the
624 complete list of EMA questions (i.e., paranoia: Q1; social functioning: Q3, Q4, Q5, Q6, Q7, Q14,
625 Q15). Adherence was monitored remotely via a secure platform, and participants who missed 3
626 consecutive surveys were contacted by research personnel to identify and resolve any issues.
627 Compensation of the EMA periods was determined by the actual number of surveys completed
628 to encourage adherence.

629 A total of 47 (out of 50) participants had full data across three EMA periods. One
630 participant did not have a phone and chose not to participate in the EMA protocol. Two
631 participants completed baseline EMA but lost their phones afterwards, and thus chose not to
632 complete the two remaining EMA periods. EMA compliance in the current study was above 80%
633 across the three periods (EMA1 = 82.74%, EMA2 = 83.38%, EMA3 = 80.04%).

634

635 **9. Statistical Analyses Plan**

636 For all tests, a conventional threshold of $\alpha = 0.05$ was used. While opting not to correct
637 for multiple comparisons may permit alpha inflation, we did not want to risk missing any
638 potential therapeutic effects in this treatment study by increasing the likelihood of Type II errors.
639 Therefore, in line with a large body of existing literature, findings that passed the significance
640 level of $\alpha = 0.05$ are presented.

641 **Hypothesis 1a:** To test the reduction in paranoia measured in the lab (active vs. sham
642 stimulation), repeated-measures ANOVAs were performed for self-reported state paranoia
643 measured both before and after the stimulation, while paired-samples t-tests were performed for
644 paranoia-related outcomes measured only after stimulation (i.e., attributional bias and hostility,
645 trust to strangers).

646 **Hypothesis 1b:** Multilevel modeling (MLM) with maximum likelihood robust estimation was
647 used to test the differences in daily feelings of paranoia (i.e., Q1) across the three EMA periods
648 (EMA-baseline vs. EMA-active vs. EMA-sham), with the condition of the EMA period being
649 dummy-coded.

650 **Hypothesis 2a:** To test the improvement in social functioning measured in the lab (active vs.
651 sham stimulation), paired-samples t-tests were performed for self-reported social functioning
652 measured only after the stimulation.

653 **Hypothesis 2b:** MLM with maximum likelihood robust estimation was used to test the
654 differences in daily social functioning (i.e., Q3, Q4, Q5, Q6, Q7, Q14, Q15) across the three
655 EMA periods (EMA-baseline vs. EMA-active vs. EMA-sham), with the condition of the EMA
656 period being dummy-coded.

657 Notably, one of the daily social functioning questions (i.e., Q3: Since the past alarm, who
658 have you interacted with?) has a different score range. It is quantified as the frequency of social
659 interactions, where a higher score indicates more interactions across a broader range of people
660 categories (range = 0-5). In contrast, the remaining six items adhere to a score range of 1-7.
661 Therefore, we performed MLM separately for Q3 (named as social interaction frequency) and for
662 the average of items Q4, Q5, Q6, Q7, Q14, and Q15 (named as social interaction motivation and
663 experience) for parsimony.

664

665 **10. Participant Payment**

666 Participants were compensated \$20 for completing the enrollment visit, \$100 for each of
667 the two in-lab stimulation visits, and up to \$16 for each of the 7-day EMA periods (three EMA
668 periods in total), totaling a maximum of \$268. Participants who enrolled in the study but were
669 found ineligible during screening were still compensated \$20. If participants stopped taking part
670 in the study or were withdrawn by the research team, they received \$5 for each 20 minutes
671 completed during the lab visits. For example, if they completed 1 hour of the study, they were
672 paid \$15. Compensation for each EMA period was determined by the number of surveys
673 completed, with \$0.75 paid for each survey except for the final survey, which was worth \$1 (to
674 allow for an even amount of \$16 per EMA period if all 21 surveys were completed). Parking on
675 campus was provided for participants.
676

677 **11. Risk and Benefits Assessments**

678 *11.1 Potential Risks*

679 It is possible that participants may feel tired, fatigued or anxious during the research
680 procedure; however frequent breaks were built into the lab portion of the study to reduce this
681 possibility. Additionally, participants were informed that they may take a break or terminate their
682 participation at any time. The most common side effect of tDCS neurostimulation is skin redness
683 just beneath the electrode. This effect usually wears off within one hour. Other potential risks
684 associated with tDCS include:

- 685 1. Itching at the electrode location; typically lasting less than an hour;
- 686 2. A small percentage of participants may experience mild dizziness upon stimulation onset.
687 After stimulation, this only lasts a few seconds and has no effect on balance;
- 688 3. Occasionally, temporary skin damage may occur beneath the electrode. This results in a week-
689 long darkening of the skin. At the planned current, the size of these marks, should they occur, is
690 only a few millimeters, posing a low risk;
- 691 4. After neurostimulation and the waiting period, participants may feel drowsy, but this effect
692 dissipates within one hour.

693 Finally, whenever information is gathered, there is a potential risk of loss of
694 confidentiality. This cannot be guaranteed, but every effort has been done to protect the privacy
695 of participants' information. Participants were assigned a random number that was used to
696 identify their data, and the file linking the number to the participants' email addresses and
697 birthdates was stored separately from the data they provide. This file will be erased upon
698 completion of the study. All data is stored in locked filing cabinets in secure offices at UTD, as
699 well as on password-protected/encrypted computers at UTD, and only study personnel who have
700 received extensive training in methods to protect confidentiality have access to the data.

701 *11.2 Potential Benefits*

702 It is possible that neurostimulation may reduce paranoid ideation and/or improve social
703 functioning for participants after active stimulation. However, the effects of tDCS are often
704 temporary, and we do not anticipate that such a short-term stimulation will have a lasting effect.
705 If this study is effective, subsequent research can investigate the ideal frequency and duration of
706 neurostimulation to deliver direct, long-lasting benefits.

707 This project may lay the foundation for distributing large-scale, easy-to-deliver
708 standardized treatments for patients. Additionally, this study's use of ecological momentary
709 assessments (EMA) will facilitate a better understanding of how treatment effects can be

710 observed in, and impacted by, real-world social situations, thereby laying the groundwork for
711 elucidating the duration of real-world improvements and developing potential long-term
712 treatment gains for individuals with schizophrenia.

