371 stimulation condition relative to sham stimulation as measured by *EMA assessments* (i.e., more
372 interactions with others, more positive experience in, and expectations of, daily social
373 interactions).

374 4. Participants

375 A total of 62 participants (age = 18-64) diagnosed with schizophrenia or schizoaffective
376 disorder with current (in the past week) or recent (in the past month) paranoia were enrolled in
377 the study. Twelve participants withdrew ($n = 4$), were lost to follow-up ($n = 7$), or were
378 determined ineligible after the enrollment visit ($n = 1$), resulting in 50 participants completing
379 the whole procedure (see **Table 1** in the main article). Non-completers did not differ
380 significantly from the completed sample in age ($p = 0.813$), gender ($p = 0.693$), race ($p = 0.321$),
381 ethnicity ($p = 0.970$), IQ ($p = 0.322$), years of education ($p = 0.538$), handedness ($p = 0.861$), or
382 CPZ-equivalent ($p = 0.176$). However, a higher proportion of non-completers were not taking
383 any medications for their mental disorders ($n_{\text{Not-taking medication}} = 8$, 66.66% of the subsample)

384 compared to completers ($n_{\text{Not-taking medication}} = 3$, 6.00% of the subsample; $\chi^2 (1) = 24.41$, $p <$
385 0.001), suggesting a lower adherence to treatment and possibly more severe psychopathological
386 symptoms in this population. Supporting this notion, more non-completers showed current
387 paranoia ($n_{\text{current paranoia}} = 12$, 100.00% of the subsample) compared to completers ($n_{\text{current paranoia}} =$
388 38, 76.00% of the subsample; $\chi^2 (1) = 3.57$, $p = 0.059$) at a marginally significant level.

389 4.1 Sample Size Estimation

390 In our pilot study using an undergraduate sample, a medium effect size was revealed in
391 the active stimulation group (Cohen's $d = 0.51$), thus it was used for sample size estimation
392 using G*Power 3.1 (Faul et al., 2009) in the current study. For research goals 1 and 2, we
393 planned to use repeated-measures ANOVAs to test the tDCS effects on VLPFC on paranoia and
394 social functioning, and power analyses yielded a sample size of 46 in total ($\beta = 0.25$, power =

396 0.80, $\alpha = .05$, correlation among repeated measures = 0.3) in order to detect a medium effect.
397 Given the potentially high retention rate due to the repeated-stimulation characteristics of this

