398 study, we intentionally overrecruited. Recruitment continued until the end of January 2024,
399 aligning with the anticipated completion of our data collection period. As a result, a total of 63
400 participants consented, 50 of whom were randomized and completed the study.

401 *4.2 Recruitment and Eligibility*

[figure not shown]
402 The current sample was recruited from a database of previous participants in our lab and
403 via mental health agencies in the Dallas-Fort Worth region. Study fliers were placed in outpatient
404 clinics, and interested individuals either contacted study personnel directly or asked to be
405 contacted by the study team. This recruitment approach has been consistently used by our
406 research team supervised by [name], and has been found to yield a substantial number
407 of participants, respect patient privacy, and minimize the possibility of coercion.

408 Eligible participants were between the ages of 18 and 64 inclusively, had a diagnosis of
409 schizophrenia or schizoaffective disorder, and demonstrated either current (in the past week) or
410 recent (in the past month) paranoia. Participants were not asked to change any part of their
411 current treatment regimen, and all medications were accepted. Participants were required to have
412 been clinically stable for a minimum of 6 weeks with no dose changes $>20\%$ for a minimum of
413 two weeks. Exclusion criteria included: 1) presence or history of a pervasive developmental
414 disorder or mental retardation as defined by $IQ < 70$, 2) presence or history of neurological or
415 medical disorders that contraindicate neural stimulation (e.g. presence or history of epilepsy,
416 seizures, etc.), 3) demonstrating sensory limitations, including uncorrectable visual or hearing
417 impairments that interfere with assessment, 4) history of electroconvulsive therapy, 5) lack of
418 proficiency in English, and 6) substance use disorder not in remission in the past 6 months.

419
420 **5. Procedure**

421 As shown in **Figure 1** below, this was a double-blind, within-subjects, crossover design
422 comparing the effects of active vs. sham tDCS. Participants completed 3 long visits (i.e., 1
423 enrollment visit, 2 stimulation visits). The 2 stimulation visits were at least a week apart (with an
424 average of 14.58 days between the stimulation visits in the current study) to make sure that the

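### The paired t-tests for in-lab outcomes measured once per visit have no visit term, so any Visit 1 to Visit 2 shift makes them conservative although order was randomised and recorded

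*Combined protocol and SAP*

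**What the plan says.** Section 6.2 (Counterbalance and Randomization) describes a two-condition crossover in which the device allocated the order at random. Of the 50 completers, 26 "received the active stimulation at their Visit 1, while the remaining 24 received it at their Visit 2". Each participant's condition at each visit was recorded after study completion. Section 5 sets a gap of at least a week between stimulation visits (mean 14.58 days) and justifies it as time for the tDCS effect to fade.

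Section 9 assigns the in-lab analyses. Under Hypothesis 1a, repeated-measures ANOVA is used for state paranoia "measured both before and after the stimulation, while paired-samples t-tests were performed for" paranoia-related outcomes taken only after stimulation. By the assessment sections these are AIHQ, SST, PID-5-HS and the trustworthiness task, although the parenthesis in section 9 does not name the SST separately. Under Hypothesis 2a, paired t-tests are used for social functioning (SFS), which section 7.3 shows is taken once per visit. No visit, period or sequence term is named for any in-lab outcome, and no sensitivity analysis for order. On the error rate: "For all tests, a conventional threshold of $\alpha = 0.05$ was used".

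**The concern.** In a two-period crossover, a change from Visit 1 to Visit 2 that has nothing to do with stimulation (familiarity with the tasks, a time trend) lowers the active-minus-sham difference in one sequence and raises it by the same amount in the other. Counterbalancing nearly cancels this in the mean. It does not remove it from the spread of the differences, and the paired t-test estimates its standard error from that spread. The washout gap is aimed at the stimulation effect and does not address practice or time.

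What is at stake is power and the width of the intervals. Section 9 declines multiplicity correction expressly to limit Type II errors, so a test that can become conservative without anyone noticing works against the plan's own aim and makes a null in-lab result harder to read.

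**Working it through.** **The plan's own figure.** Section 4.1 states: "social functioning, and power analyses yielded a sample size of 46 in total ($\beta = 0.25$, power" set at "0.80, $\alpha = .05$, correlation among repeated measures = 0.3) in order to detect a medium effect". The 0.25 reproduces 46 only if read as Cohen's f (for two conditions d = 2f = 0.5, next to the pilot's 0.51); a power of 0.80 would imply a Type II error of 0.20. With two measurements and one group, λ = N × 2 × f² / (1 − ρ) = 46 × 2 × 0.0625 / 0.7 = 8.21 on (1, 45) df, and power is 0.801. N = 45 gives 0.792, so 46 is reproduced. At the analysed N = 50, λ = 8.93 and power is 0.834.

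**Inputs.** n₁ = 26 active-first and n₂ = 24 sham-first (section 6.2); ρ = 0.3 (section 4.1); τ = 0.5 outcome SD; α = 0.05, taken as two-sided because sidedness is not stated. The visit shift π, in outcome SDs, is **assumed** at 0.2, 0.3 and 0.5; the documents give no value.

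**Mechanism.** Orient each outcome so that τ > 0 favours active, and let D = active − sham.
- E(D) = τ − π in the 26 active-first and τ + π in the 24 sham-first.
- Bias of the paired mean = π × (24 − 26)/50 = −0.04π.
- True within-sequence variance of D = 2(1 − 0.3) = 1.4, so the sampling SD of the paired mean is √(1.4/50) = 0.167, whatever π is.
- The variance that the t-test estimates rises by 4π² × 26 × 24/(50 × 49) = 1.019π².
- For π = 0.5: 1.019 × 0.25 = 0.255, and 0.255/1.4 = 18.2%.
- Visit-adjusted estimate = mean of the two sequence means of D, with SE = (√1.4/2) × √(1/26 + 1/24) = 0.1675 on 48 df and no bias from π.

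**Results.** Power and Type I error are from simulation at N = 50, split 26/24.

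| Assumed shift π (outcome SD) | Size of bias (SD) | Rise in estimated variance of D | Estimated SE (true 0.167) | Paired-t power, unfavourable / favourable sign | Visit-adjusted power | Paired-t Type I error |
|---|---|---|---|---|---|---|
| 0.2 | 0.008 | 2.9% | 0.170 | 0.81 / 0.84 | 0.83 | 0.047 |
| 0.3 | 0.012 | 6.6% | 0.173 | 0.80 / 0.84 | 0.83 | 0.044 |
| 0.5 | 0.020 | 18.2% | 0.182 | 0.75 / 0.82 | 0.83 | 0.035 |

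The visit-adjusted test keeps a Type I error of 0.05 throughout. The unfavourable sign is improvement from Visit 1 to Visit 2, because slightly more participants had active stimulation first. If there is no shift, adjustment lowers power from 0.8337 to 0.8328.

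**Sensitivity to the correlation.** A higher within-person correlation makes the same shift matter more relative to the error: at an assumed ρ of 0.7 the variance rises by 6.8%, 15.3% and 42.4%. Power at d = 0.5 is then high in any case (0.974 against 0.994 at π = 0.5, unfavourable sign).

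**State paranoia.** SSPS is taken before and after stimulation at each visit. Section 9 does not say which ANOVA effect is the test. If it is condition-by-time, a constant visit shift cancels in the pre-post change, and only a difference between visits in that change remains. If it is the condition main effect, the whole shift stays in. The table applies to the outcomes measured once per visit, not to a condition-by-time test of SSPS.

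**The case against.** The best defence is that counterbalancing has done its work. The bias is 4% of any shift, its expectation over the randomisation is zero, and the error runs in the safe direction: no false positive is created. All of that stands.

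It is also fair to say that no visit effect is documented. Participants had to be clinically stable for six weeks. Paranoia was screened at enrolment, on average 13.59 days before the first stimulation visit, so some regression to the mean would come before both analysed visits. AIHQ and face-trust ratings have no correct answer to learn. Section 6.7 says "Five ambiguous scenarios were presented to participants" but not whether the same five were used twice. A reader might infer that drift to lower scores is to be expected; the documents support only that it is possible.

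A reader might also treat the larger estimated variance as equivalent to losing participants. It is not: the sampling SD of the paired mean stays at 0.167, and only the estimated standard error rises. Nor should very large losses be read in. Power near 0.58 needs a shift of 0.8 SD of the paired difference, which is 0.8 × √1.4 = 0.95 outcome SD at the plan's correlation, and nothing in the documents points to that.

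Finally, recruitment ended in January 2024 and the plan is written in the past tense, so replacing a stated test now would be a change after data collection. That is a reason to show both analyses, not to omit the adjusted one. None of these points answers the precision argument: balance protects the mean, not the estimated standard error.

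**Conclusion.** The point holds for the in-lab outcomes measured once per visit: AIHQ, SST, PID-5-HS and trust (Hypothesis 1a) and SFS (Hypothesis 2a). Without a visit term, any additive visit shift makes the paired t-test conservative. The cost is modest: at assumed shifts of 0.2 to 0.5 outcome SD, about 2 to 8 percentage points of power in the unfavourable direction, from 1 point lost to a fraction of a point gained in the favourable one, and Type I error between 0.047 and 0.035. These figures rest on the plan's ρ of 0.3, d = 0.5, normal outcomes and the assumed shifts.

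A reader might go further and infer that the in-lab results are biased or that positive findings are unsafe. The documents do not support that: the bias is at most 0.02 SD in the range examined, and the test rejects too seldom, not too often. Nor does the point carry over unchanged to SSPS, where it depends on the ANOVA effect tested. The change is worth making because it follows the design that was randomised and costs almost nothing.

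**What to change.** In section 9, analyse the outcomes measured once per visit with the standard two-period crossover model: condition, visit and sequence as fixed effects and a participant random intercept. With complete pairs this is equivalent to comparing Visit 1 minus Visit 2 differences between the two sequences. For SSPS, state which ANOVA effect is the test and add visit and visit-by-time to the model. Because data collection is complete, report the stated paired t-tests alongside and label the adjusted analysis as added.

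Cost: SAP wording and a re-run on data already recorded, one degree of freedom, and about 0.1 percentage point of power if there is no visit effect. This does not address carry-over, which needs separate consideration.
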